9.1.5 Vital Signs

Body temperature, blood pressure, pulse and respirations will be performed after resting for 5 minutes on each scheduled visit.

9.1.6 Adverse Events

Information regarding occurrence of adverse events will be captured throughout the study. Duration (start and stop dates), severity/grade, outcome, treatment and relation to study drug will be recorded on the case report form (CRF).

9.2 Clinical Laboratory Measurements

9.2.1 Urinalysis

Urine will be obtained and sent to each site's clinical laboratory for determination of color, specific gravity, pH, protein, glucose, ketones, and blood

Urine will be collected for ICP-OES assessment of sulfur.

10 EVALUATIONS BY VISIT

10.1 Visit 1 (Day 0)

1. Review the study with the subject (subject's legal representative) and obtain written informed consent and HIPAA authorization.
2. Assign the subject a unique screening number.
3. Record demographics data.
4. Record medical history, including a history of cystinuria, diagnosis date, and prior treatments.
5. Record concomitant medications.
6. Perform a complete physical examination.
7. Perform and record vital signs.
8. Perform and record results of blood pressure testing.
9. Schedule subject for Visit 2 in 28 days.

SGLT2-02, [name]

10. Collect urinalysis.
11. Collect freshly voided urine samples and obtain baseline analysis using mass spectrometry.
12. Prescribe study drug and provide a participant diary.

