4 STUDY DESIGN

4.1 Study Overview

This is a single center, proof of concept prospective cohort trial designed to assess the effect of daily oral administration of dapagliflozin 10 mg on cystine formation in freshly voided urine. Ten subjects are planned, each with previously diagnosed cystinuria and without current treatment except with potassium citrate medication.

SGLT2-02, [name]

Each subject will have an initial visit during which screening data will be reviewed to determine subject eligibility. Subjects who meet all inclusion criteria and none of the exclusion criteria will be entered into the study. Consent will be obtained as well as an initial examination and collection/analysis of freshly voided urine with mass spectrometry to serve as a baseline. The therapy under investigation, dapagliflozin 10 mg, will then be administered orally to each participant daily for four weeks, at which time each subject will return for a second visit for an analysis of freshly voided urine using mass spectrometry. The different urine collections will be compared and analyzed for differences with the prescribed therapy. No placebo will be used during this proof-of-concept study.

Total duration of subject participation will be up to six weeks. Total duration of the study is expected to be six weeks.

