8.2 Blinding

This is a nonblinded proof of concept study.

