10.2 Visit 2 (Day 28)

1. Record any Adverse Experiences and/or Review subject diary for adverse experiences and dosing compliance.
2. Concomitant medications review.
3. Perform abbreviated physical examination.
4. Perform and record vital signs.
5. Collect urinalysis.
6. Collect freshly voided urine samples and obtain treatment analysis using mass spectrometry.

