14.1 Data Sets Analyzed

Data sets from all participants enrolled in the study will be analyzed. The primary efficacy endpoint will be assessed by medical history and physical exam, in addition to mass spectrometry data obtained at each study visit.

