14.3 Analysis of Primary Endpoint

The primary endpoint will be analyzed through quantitative comparison between the baseline urine mass spectrometry analysis and the treatment urine mass spectrometry analysis.

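### Each subject's two urine samples are analysed 28 days apart with no control arm and no shared assay material, so a common or one-directional assay shift would be added to the estimated treatment effect

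*Combined protocol and SAP*

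**What the plan says.** The visit lists treat the measurement as part of the visit. Section 10.1 has the site "Collect freshly voided urine samples and obtain baseline analysis using mass spectrometry" on Day 0 and then "Schedule subject for Visit 2 in 28 days". Section 10.2 has it "Collect freshly voided urine samples and obtain treatment analysis using mass spectrometry" on Day 28. Section 4.1 agrees: after four weeks on drug "each subject will return for a second visit for an analysis of freshly voided urine using mass spectrometry". Section 14.1 refers to "mass spectrometry data obtained at each study visit", and Appendix 1 marks the analysis once under each visit.

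Section 4.1 also states that "No placebo will be used during this proof-of-concept study". Section 14.3 defines the primary analysis as a "quantitative comparison between the baseline urine mass spectrometry analysis and the treatment urine mass spectrometry analysis". The synopsis gives the endpoint as urinary sulfur by ICP-OES in fresh urine, with 10 subjects.

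The documents do not mention stored aliquots, joint assay of pairs, common calibrators, quality-control pools, replicates or re-assay of baseline samples. Section 9.2.1 says only that urine is collected for the ICP-OES sulfur measurement.

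**The concern.** The only efficacy contrast is the Visit 2 reading against the Visit 1 reading in treated subjects. If the instrument, its calibration, the reagents or the sample handling differ between those two occasions, the difference enters each subject's change alongside any drug effect. A concurrent control group would show the same shift and allow it to be subtracted; this design has none. The part of a shift that subjects share does not shrink as subjects are added, and no later analysis can recover it without common material measured on both occasions. At stake is the estimate that decides whether the sponsor goes on to a larger study.

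**Working it through.** **The plan's own figure.** There is none to reproduce. Section 14.5 gives a sample size of ten without an alpha, power, effect size, SD or test, and no assay precision is stated anywhere.

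**Structure.** For subject *i*, observed change = true change + (assay error at Visit 2 − assay error at Visit 1) + biological variation. Averaged over subjects, any part of the bracket that they share stays in full, while independent parts average down as 1/√n.

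**Inputs.** From the documents: n = 10, an interval of 28 days, no control. Assumed: a two-sided 5% paired t-test; a within-subject CV of 10% to 50% for a single voided sample; a common shift of 5% or 10%.

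**Case A: a fixed shift b common to all Visit 2 measurements.**
- SD of the paired difference = CV × √2. At a 10% CV this is 14.1%.
- SE of the mean change = SD/√10. At a 10% CV this is 14.1/3.162 = 4.5%.
- Noncentrality = b/SE. For b = 5% at a 10% CV this is 5/4.47 = 1.12.
- False-positive rate = P(|T| > 2.262), with T noncentral t on 9 df.

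| Within-subject CV | SE of mean change | Rate, 5% shift | Rate, 10% shift |
|---|---|---|---|
| 10% | 4.5% | 17.1% | 51% |
| 20% | 8.9% | 7.9% | 17.1% |
| 30% | 13.4% | 6.3% | 10.3% |
| 40% | 17.9% | 5.7% | 7.9% |
| 50% | 22.4% | 5.5% | 6.9% |

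A 3% shift gives 9.2% at a 10% CV and at most 5.5% at CVs of 30% or more. In every row the point estimate carries the whole shift, whatever the test does.

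**Case B: random run effects (200,000 simulations per setting).** Here the SD of change is set directly, and a between-run CV applies to each run.
- One shared run per visit, SD of change 30%: the rate is 5.8%, 10.2% and 24.0% at run CVs of 2%, 5% and 10%. Over SDs of 20% to 40% and the same run CVs it ranges from 5.5% to 38.0%.
- A separate, independent pair of runs for each subject: the rate stays at about 5%. At SD 30% and run CV 5%, the SE rises only from 30/√10 = 9.49 to √((30² + 2×5²)/10) = 9.75 points.
- Both samples of a subject in the same run: the shift cancels, the rate is about 5%, and the SE is 9.49 points.

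The harm therefore depends on whether the shift is shared across subjects and on how noisy a single voided sample is.

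**The case against.** **The timing is inferred.** The visit lists are checklists, and no section mentions runs or batches or forbids joint assay. The statistical analysis plan still to be written, or a laboratory manual, could settle it. This is fair, but every section that touches timing places the measurement at the visit, and none provides for anything else.

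**Staff knowledge of the visit.** A reader might infer from Section 8.2 ("This is a nonblinded proof of concept study") that the analysts know which visit a sample comes from. The documents do not say so. Section 16 has all laboratory specimens labelled by coded number and initials only. That does not show that visit is masked, but it rules out asserting the opposite.

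**Clustering.** A reader might also infer from the six-week study duration in Section 4.1 that all baselines share one run period and all treatment samples a later one, so that assay error falls entirely on the treatment effect. That requires all ten subjects to enter almost together. Other sections allow staggering: a single site, a rare disease, replacement of withdrawals (Section 12.4), and a safety look when about half have completed Visit 2 (Section 14.4). Under staggered entry, independent run errors become noise. Only a common shift or a one-directional drift still biases the result.

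**Size.** The 17% figure needs low biological noise, and the test is the reviewer's assumption. This stands, and the table shows the full range.

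**Storage.** Holding only baseline aliquots for 28 days would align storage time with visit, and Section 1 describes cystine as prone to precipitate and dependent on pH. This also stands, and it changes the remedy.

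**Conclusion.** The concern holds in a limited form. As written, the plan leaves an assay shift that is common to the Visit 2 measurements, or that drifts towards them in one direction, inseparable from the drug effect, and nothing in the design would detect it. This is a structural weakness, not evidence that a shift will occur. Its size cannot be taken from the documents. Under the assumed paired t-test, a 5% common shift is material at a 10% within-subject CV, modest at 20%, and nearly lost in the noise of the test at 30% to 50%, although the estimate is still displaced by the full 5%. The documents do not support the stronger conclusions that every baseline will sit in one run period, or that the laboratory will know the visit. A change is still worthwhile, because a better layout is available at little cost and the bias cannot be removed afterwards.

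**What to change.** Amend Sections 9.2.1, 10.1 and 10.2 as follows.

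1. Keep the fresh analysis at each visit.
2. At both visits also preserve an aliquot by one identical procedure that keeps cystine in solution, or else process the whole aliquot so that any precipitate is included.
3. Measure both aliquots of a subject for total sulfur in the same ICP-OES run, in random order, under codes that do not reveal the visit.
4. Compare the fresh and stored readings of the baseline sample. Set the stability criterion in advance, and use the paired-run value as primary only if the check shows no storage loss.
5. If it fails, keep the fresh value as primary and run the same calibrators and quality-control pool at both visits, with a written rule for detecting and correcting a shift.

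The sections should also use one name for the method, since the endpoint says ICP-OES while the visit steps and Section 14.3 say mass spectrometry.

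The cost is small: about 10 aliquots stored for 28 days, one stability check and some repeat measurements. No subjects or visits are added.

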CRITERIA	history of previous cystine kidney stones; and being able and willing to provide consent Exclusion Criteria: prior diagnosis of diabetes mellitus (type I or type II); current SGLT-2 inhibitor administration at the time of screening; SGLT-2 inhibitor administration within the last year prior to screening; vulnerable populations including incarceration status; anticipation of pregnancy during the study duration; unable to give informed consent; non-English primary language; pregnancy, lactation, or child- bearing age without birth control devices; and serious illness likely to cause death within the next 5 years.
TEST PRODUCT, DOSE, AND ROUTE OF ADMINISTRATION	Dapagliflozin 10 mg administered orally once daily for 4 weeks
CONTROL PRODUCT, DOSE AND ROUTE OF ADMINISTRATION	None
DURATION OF SUBJECT PARTICIPATION AND DURATION OF STUDY	Subjects will be on study for up to 6 weeks 
• Screening: 1 week to determine eligibility• Treatment: 4 weeks after the initial visit (Day 0)• Follow-up: 1 week after the last visit (Day 28)
CONCOMMITANT MEDICATIONS	Allowed: The participants will be allowed to continue any medications they are currently taking with the exception of those listed below under “prohibited”. Importantly, patients will be allowed to continue potassium citrate as this is an important mainstay of cystinuria treatment as discontinuation may lead to clinically significant cystine stone formation. Prohibited: Medications commonly used to treat diabetes, such as but not limited to insulin, metformin, and glipizides. These medications may interfere with the action of SGLT-2 inhibitors by altering the manner in which the body metabolizes and regulates glucose. Medications commonly used to treat cystinuria: thiola, penicillamine, alpha lipoic acid
EFFICACY EVALUATIONS	Efficacy in this study will be determined by utilizing mass spectrometry to analyze for the presence of sulfur in the urine before and after initiation of therapy with SGLT-2 inhibitor in our patients with cystinuria. Urinary cystine levels on 24-hour urine collection will also be measured.
PRIMARY ENDPOINT	Quantitative urinary sulfur via inductively coupled plasma optical emission spectroscopy (ICP-OES) in freshly voided urine

SGLT2-02, [name]

OTHER EVALUATIONS	

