6.3 Exclusion Criteria

Pregnant, breastfeeding, or unwilling to practice birth control during participation in the study; Presence of a condition or abnormality that in the opinion of the Investigator would compromise the safety of the patient or the quality of the data; Diagnosis of diabetes mellitus (type I or type II); Current SGLT-2 inhibitor administration at the time of screening or SGLT-2 inhibitor administration within the last year prior to screening; Vulnerable populations including incarceration status; Anticipation of pregnancy during the study duration; Unable to give informed consent; Non-English primary language; pregnancy, lactation, or child- bearing age without birth control devices; Serious illness likely to cause death within the next 5 years.

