9 STUDY PROCEDURES AND GUIDELINES

A Schedule of Events representing the required testing procedures to be performed for the duration of the study is diagrammed in Appendix 1.

Prior to conducting any study-related activities, written informed consent and the Health Insurance Portability and Accountability Act (HIPAA) authorization must be signed and dated by the subject or subject's legal representative. If appropriate, assent must also be obtained prior to conducting any study-related activities.

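### Pregnancy is an exclusion, but no pregnancy test is required before the drug is prescribed at Visit 1

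*Combined protocol and SAP*

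**What the plan says.** Men and women aged 18 or older may enrol. Section 6.3 excludes anyone "Pregnant, breastfeeding, or unwilling to practice birth control during participation in the study", and later in the same list "pregnancy, lactation, or child- bearing age without birth control devices". It also excludes women who expect to become pregnant during the study. The synopsis carries similar criteria.

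On how eligibility is established, the synopsis gives "Screening: 1 week to determine eligibility", and Section 4.1 says that at the initial visit "screening data will be reviewed to determine subject eligibility". Neither lists what the screening data contain. Section 9 begins its consent rule with "Prior to conducting any study-related activities, written informed consent", and consent is step 1 of Visit 1.

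On testing, Section 9 states: "A Schedule of Events representing the required testing procedures to be performed for the duration of the study is diagrammed in Appendix 1". Section 9.2.1 sends urine to the clinical laboratory "for determination of color, specific gravity, pH, protein, glucose, ketones, and blood", with a further collection for sulfur by ICP-OES. Visit 1 ends at step 12: "Prescribe study drug and provide a participant diary". Section 8.4.2 provides a four-week supply of 28 tablets, and the next clinic visit is Day 28.

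The only visible mention of a pregnancy test is in Section 12.1, where a positive result is among the possible reasons for stopping study drug.

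**The concern.** The plan has already decided that pregnant women should not receive dapagliflozin in this study. As written, it applies that decision through history, self-report, examination and the birth-control requirement. Birth control makes pregnancy less likely, but it does not detect a pregnancy that already exists, whether from contraceptive failure or from conception before birth control began.

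Section 12.1 makes the gap more visible: it acts on a test result that no scheduled procedure would produce. Because the whole course is supplied at once and there is no clinic visit before Day 28, nothing scheduled in between is designed to find the pregnancy. The 1-week contact asks about compliance, tolerability and side effects.

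What is at stake is the safety of a participant and the plan's ability to enforce its own exclusion.

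**Working it through.** The plan gives no figure to reproduce. The check is a count of every place where a test could be required, then a bound on exposure, then an illustration of likelihood.

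**Where a test could appear**

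| Place | Items | Items naming a pregnancy test |
|---|---|---|
| Section 9.2.1, urinalysis determinations | 7 | 0 |
| Section 10.1, Visit 1 steps | 12 | 0 |
| Section 10.2, Visit 2 steps | 6 | 0 |
| Appendix 1, rows | 15 | 0 |

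The ICP-OES sulfur measurement in Section 9.2.1 is additional to the seven determinations and is not a pregnancy test either. The synopsis and Sections 4.1, 6.2 and 6.3 name no test.

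**Order of events at Visit 1.** Consent is step 1, history step 4, physical examination step 6, urine collection steps 10 and 11, and prescribing step 12. Urine is therefore in hand before the drug is prescribed, but nothing in steps 1 to 11 calls for a pregnancy test.

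**Exposure if a pregnancy is missed.** One tablet daily with 28 tablets supplied (Sections 8.4.2 and 8.4.3) gives up to 28 doses. If a Visit 1 test detects the pregnancy before step 12, the number is 0 of 28.

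**Likelihood (assumptions only).** Let *k* be the number of enrolled women of child-bearing potential and *p* the chance that such a woman, using birth control, has an unrecognised pregnancy at Visit 1. The documents give neither. Taking *p* from 0.001 to 0.01 for illustration:

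P(at least one) = 1 − (1 − *p*)^*k*

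- *k* = 1: 0.1% to 1.0%
- *k* = 5: 1 − 0.999^5 = 0.5%, to 1 − 0.99^5 = 4.9%
- *k* = 10: 1 − 0.999^10 = 1.0%, to 1 − 0.99^10 = 9.6%

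The last line is an extreme: it needs all ten subjects to be women of child-bearing potential, although both sexes are eligible and there is no upper age limit.

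**The case against.** The strongest reply is that other safeguards exist and that the documents' silence does not prove that no test will be done.

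- **Other safeguards.** Women must use birth control, those anticipating pregnancy are excluded, and the investigator may exclude anyone whose condition would compromise safety. Medical history and a complete physical examination precede prescribing, and a physician prescribes. After that there is a coordinator contact at 1 week and a 24-hour physician telephone number. These should catch a known or suspected pregnancy. They would not reliably catch an early, unrecognised one.
- **Screening data.** A pregnancy result from ordinary care could be among the data reviewed, and the consent rule would not bar looking at it. That is possible, but nothing asks for such a result. A test ordered for the study before Visit 1 would precede consent.
- **Incomplete lists.** Appendix 1 also omits the 1-week contact and the 24-hour urine cystine, so its silence alone proves little. Section 11.1 refers to a separate study manual that is not part of these documents, and the Medical Monitoring section named in the contents is not visible, though that is an unlikely place for a Visit 1 test. This limits the claim to visible text. The finding does not depend on the appendix, because Sections 9.2.1, 10.1 and 10.2 are silent too.
- **Harm and size.** The documents describe no specific harm of dapagliflozin in pregnancy; the importance of avoiding exposure is inferred from the sponsor's own exclusion. The 28 doses are a worst case, and the probabilities rest on assumed inputs. All of this stands, and it keeps the point at a modest level.

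**Conclusion.** The concern holds. No visible text requires a pregnancy test before the drug is prescribed, although pregnancy is an exclusion and a positive test is a listed reason to stop.

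The consequence is up to 28 doses in a participant who should not have been enrolled, assuming that the pregnancy goes unnoticed and nothing else prompts stopping. The likelihood is low and cannot be derived from the documents; the percentages above only illustrate how it scales with the assumed inputs.

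The change should be made because it is cheap and makes an existing safety criterion enforceable. No result of the trial is at risk.

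**What to change.** Make three matching edits:

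1. **Section 9.2.1:** add one line for a point-of-care urine pregnancy test in women of child-bearing potential.
2. **Section 10.1:** add a step that runs this test on the urine already collected at steps 10 and 11, and require a negative result before step 12.
3. **Appendix 1:** add one row, marked at Visit 1.

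State that the test is repeated on clinical suspicion, which would also supply the result that Section 12.1 relies on. A question about possible pregnancy at the 1-week contact is optional.

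The cost is at most ten low-cost strips for the ten planned subjects, plus those for replacements and any repeats, and a few minutes before prescribing. Visit 1 needs no extra sample and the study no extra visit. A test can miss a very early pregnancy, so the birth-control criteria should stay as they are.

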10.2 Visit 2 (Day 28)

1. Record any Adverse Experiences and/or Review subject diary for adverse experiences and dosing compliance.
2. Concomitant medications review.
3. Perform abbreviated physical examination.
4. Perform and record vital signs.
5. Collect urinalysis.
6. Collect freshly voided urine samples and obtain treatment analysis using mass spectrometry.

11 ADVERSE EXPERIENCE REPORTING AND DOCUMENTATION

11.1 Adverse Events

An adverse event (AE) is any untoward medical occurrence in a clinical investigation of a patient administered a pharmaceutical product and that does not necessarily have a causal relationship with the treatment. An AE is therefore any unfavorable and unintended sign (including an abnormal laboratory finding), symptom or disease temporally associated with the administration of an investigational product, whether or not related to that investigational product. An unexpected AE is one of a type not identified in nature, severity, or frequency in the current Investigator's Brochure or of greater severity or frequency than expected based on the information in the Investigator's Brochure.

The Investigator will probe, via discussion with the subject, for the occurrence of AEs during each subject visit and record the information in the site's source documents.

Adverse events will be recorded in the patient CRF. Adverse events will be described by duration (start and stop dates and times), severity, outcome, treatment and relation to study drug, or if unrelated, the cause.

AE Severity

The National Cancer Institute's Common Terminology Criteria for Adverse Events (CTCAE) Version 3.0 should be used to assess and grade AE severity, including laboratory abnormalities judged to be clinically significant. The modified criteria can be found in the study manual. If the experience is not covered in the modified criteria, the guidelines shown in Table 1 below should be used to grade severity. It should be pointed out that the term "severe" is a measure of intensity and that a severe AE is not necessarily serious.

Table 1. AE Severity Grading

Severity (Toxicity Grade)	Description
Mild (1)	Transient or mild discomfort; no limitation in activity; no medical intervention or therapy required. The subject may be aware of the sign or symptom but tolerates it reasonably well.
Moderate (2)	Mild to moderate limitation in activity, no or minimal medical intervention/therapy required.
Severe (3)	Marked limitation in activity, medical intervention/therapy required, hospitalizations possible.
Life-threatening (4)	The subject is at risk of death due to the adverse experience as it occurred. This does not refer to an experience that hypothetically might have caused death if it were more severe.

AE Relationship to Study Drug

The relationship of an AE to the study drug should be assessed using the following the guidelines in Table 2.

Table 2. AE Relationship to Study Drug

Relationship to Drug	Comment
Definitely	Previously known toxicity of agent; or an event that follows a reasonable temporal sequence from administration of the drug; that follows a known or expected response pattern to the suspected drug; that is confirmed by stopping or reducing the dosage of the drug; and that is not explained by any other reasonable hypothesis.
Probably	An event that follows a reasonable temporal sequence from administration of the drug; that follows a known or expected response pattern to the suspected drug; that is confirmed by stopping or reducing the dosage of the drug; and that is unlikely to be explained by the known characteristics of the subject's clinical state or by other interventions.
Possibly	An event that follows a reasonable temporal sequence from administration of the drug; that follows a known or expected response pattern to that suspected drug; but that could readily have been produced by a number of other factors.
Unrelated	An event that can be determined with certainty to have no relationship to the study drug.

